7.4.2 Visit 1: Dispensing visit

Dispensing visit may occur on same day as Visit 0. In which case, steps 1,2 &3 are redundant.

1. Entrance distance HHHC VA (OD, OS) with best spherocylindrical correction.
2. Slit lamp biomicroscopy will be assessed according to the criteria set out in the Appendix 2.
 - a. Not required if done in combination with Visit 0.
3. The investigator will confirm that the patient meets the criteria set out in the inclusion criteria.
4. The first pair of lenses will be inserted by the subject according to randomization schedule.
5. Initial contact lens power chosen based on vertexed, spherical equivalent obtained from refraction.
6. The initial lens fit will be assessed for fit acceptance (acceptable or not acceptable). If the fit is acceptable, the subject will be allowed to sit in the waiting area for a minimal of 10 minutes to allow for the lenses to settle.
7. Visual acuity with initial contact lens power will be assessed.
 - a. Distance visual acuity
 - i. High Illumination High Contrast (OU)
 - ii. Low Illumination High Contrast (OU)
 - b. Near visual acuity
 - iii. High Illumination High Contrast (OU)
 - iv. Low Illumination High Contrast (OU)
8. After lens settling a standard distant monocular over-refraction will be performed. The endpoint of this over refraction will be the best objective acuity and subjective acuity improvement.
 - a. Up to -0.50D will be given if objective visual acuity is improved.
 - b. -0.25D will be given if subjective visual acuity is significantly improved.
9. A lens change will be implemented if over-refraction dictates. The replacement lens will be allowed to settle for 10 minutes.
10. Change lens prescription to that noted by over-refraction, if needed.
11. Visual Acuity will be assessed with the final lens powers.
 - c. Distance visual acuity
 - v. High Illumination High Contrast (OU)
 - vi. High Illumination Low Contrast (OD, OS, OU)

vii. Low Illumination High Contrast (OD, OS, OU)

d. Near visual acuity

viii. High Illumination High Contrast (OU)

ix. Low Illumination High Contrast (OU)

High Illumination: Overhead lights on, Ideal: 60cd/m², Range: 120-200cd/m²

Low Illumination: Overhead lights off, Ideal: Ideal: 3cd/m², Range: 1-5cd/m²

[REDACTED]

[REDACTED]

14. The subject will be instructed to wear lenses for a minimal of 8 hours/day and every day until the subject come back for the follow-up visit.

15. The subject will be given enough lenses including spares to last them until the next visit.

16. The subject will be discharged and scheduled to come back for the follow-up visit wearing the study lenses for at least two hours within the required visit window.

17. The subject will be instructed to come back for the follow-up visit wearing the study lenses for at least two hours prior to the visit time.

7.4.3 Visit 2: Follow up lens pair 1/Dispensing lens pair 2 (3 days +2 days from Visit 1)

Subjects should attend wearing the study lenses, which should have been in situ for at least two hours. Subjects who attend without lenses in situ for at least two hours will be rescheduled. The following procedures will be performed (any ocular measurement procedures outlined below will be carried out on each eye):

1. Average Wear Time; Wear Time at visit; Problems and Comments will be recorded.

2. Subjects will return any unworn lenses and problem lenses.

[REDACTED]

[REDACTED]

[REDACTED]

5. Visual Acuity will be assessed with the contact lenses.

a. Distance visual acuity

i. High Illumination High Contrast (OU)

ii. High Illumination Low Contrast (OD, OS, OU)

iii. Low Illumination High Contrast (OD, OS, OU)

- b. Near visual acuity
 - i. High Illumination High Contrast (OU)
 - ii. Low Illumination High Contrast (OU)

High Illumination: Overhead lights on, Ideal: 60cd/m², Range: 120-200cd/m²

Low Illumination: Overhead lights off, Ideal: Ideal: 3cd/m², Range: 1-5cd/m²

6. Monocular over-refraction and High Illumination High Contrast logMAR VA @ 4m (OU) will be performed and recorded.
7. [REDACTED]
8. Lens removal and lens storage.
9. Slit lamp biomicroscopy will be assessed set out in the CVI grading scales.
10. Eyes will be rinsed.
11. The Randomised Pair 2 lenses will be fitted.
12. Initial contact lens power chosen based on vertexed, spherical equivalent obtained from refraction (i.e. match the initial power of the first pair).
13. The initial lens fit will be assessed for fit acceptance (acceptable or not acceptable). If the fit is acceptable, the subject will be allowed to sit in the waiting area for a minimal of 10 minutes to allow for the lenses to settle.
14. Visual acuity with initial contact lens power will be assessed.
 - a. Distance visual acuity
 - i. High Illumination High Contrast (OU)
 - ii. Low Illumination High Contrast (OU)
 - b. Near visual acuity
 - i. High Illumination High Contrast (OU)
 - ii. Low Illumination High Contrast (OU)
15. After lens settling a standard monocular over-refraction will be performed. The endpoint of this over refraction will be the best objective acuity and subjective acuity improvement.
 - c. Up to -0.50D will be given if objective visual acuity is improved.
 - d. -0.25D will be given if subjective visual acuity is significantly improved.
16. A lens change will be implemented if over-refraction dictates. The replacement lens will be allowed to settle for 10 minutes.
17. Change lens prescription to that noted by over-refraction, if needed.

18. Visual Acuity will be assessed with the final lens powers.

e. Distance visual acuity

- i. High Illumination High Contrast (OU)
- ii. High Illumination Low Contrast (OD, OS, OU)
- iii. Low Illumination High Contrast (OD, OS, OU)

f. Near visual acuity

- i. High Illumination High Contrast (OU)
- ii. Low Illumination High Contrast (OU)

High Illumination: Overhead lights on, Ideal: 60cd/m², Range: 120-200cd/m²

Low Illumination: Overhead lights off, Ideal: Ideal: 3cd/m², Range: 1-5cd/m²

[REDACTED]

[REDACTED]

21. The subject will be instructed to wear lenses for a minimal of 8 hours/day and every day until the subject come back for the follow-up visit.

22. The subject will be given enough lenses including spares to last them until the next visit.

23. The subject will be discharged and scheduled to come back for the follow-up visit wearing the study lenses for at least two hours within the required visit window.

24. The subject will be instructed to come back for the follow-up visit wearing the study lenses for at least two hours prior to the visit time.

7.4.4 Visit 3: Follow-up lens pair 2 and Exit (3 days +2 days from Visit 2)

Subjects should attend wearing the study lenses, which should have been in situ for at least two hours. Subjects who attend without lenses in situ for at least two hours will be rescheduled. The following procedures will be performed (any ocular measurement procedures outlined below will be carried out on each eye):

- 1. Average Wear Time; Wear Time at visit; Problems and Comments will be recorded.
- 2. Subjects will return any unworn lenses and problem lenses.

5. Visual Acuity will be assessed with the final lens powers.
 - a. Distance visual acuity
 - i. High Illumination High Contrast (OU)
 - ii. High Illumination Low Contrast (OD, OS, OU)
 - iii. Low Illumination High Contrast (OD, OS, OU)
 - b. Near visual acuity
 - i. High Illumination High Contrast (OU)
 - ii. Low Illumination High Contrast (OU)

High Illumination: Overhead lights on, Ideal: 60cd/m², Range: 120-200cd/m²

Low Illumination: Overhead lights off, Ideal: Ideal: 3cd/m², Range: 1-5cd/m²

6. Monocular over-refraction and High Illumination High Contrast logMAR VA @ 4m (OU) will be performed and recorded.

8. Lens removal and lens storage.
9. Slit lamp biomicroscopy will be assessed set out in the CVI grading scales.
10. Exit distance HHHC logMAR visual acuity with refraction from baseline visit (OD, OS, OU)
11. Exit statement signed and exit disposition recorded.

7.4.5 Summary of Visits and Procedures for the study.

Table 2 summarizes the visits and procedures for the study.

Table 2: Summary of Visits and Procedures

| | Visit 0 Screening / Baseline | Visit 1 Dispense Pair 1 | Visit 2 Follow-up P1 / Dispensing of Pair 2 | Visit 3 Follow-up P2 & Exit |
|--------------------------------------|------------------------------------|-------------------------------|---|-----------------------------------|
| Informed consent | ✓ | - | - | - |
| Meet inclusion/exclusion criteria | ✓ | - | - | - |
| History at baseline/Demographics | ✓ | - | - | - |
| Wearing time | ✓ | - | ✓ | ✓ |
| Auto-refraction & keratomtery | ✓ | - | - | - |
| Pupilometer | ✓ | | | |
| Sphero-cylindrical refraction | ✓ | - | - | - |
| LogMAR VAs with spectacle refraction | ✓ | - | - | - |
| Slit-lamp biomicroscopy | ✓ | ✓* | ✓ | ✓ |
| Instillation of lens at office | - | ✓ | ✓ | - |
| ████████████████████ | █ | █ | █ | █ |
| ████████████████████ | █ | █ | █ | █ |
| ████████████████████ | █ | █ | █ | █ |
| Spherical over-refraction (SOR) | - | ✓ | ✓ | ✓ |
| LogMAR visual acuity | - | ✓ | ✓ | ✓ |
| ████████████████████ | █ | █ | █ | █ |
| Exit VAs | - | - | - | ✓ |
| Study Exit | - | - | - | ✓ |

* Not applicable if Visit 1 occurs on the same day as Visit 0

Calibration will be done on all applicable instruments (i.e., autorefractor and keratometer) prior to the start of the study and a copy of the calibration document will be kept on file. A copy of the calibration document will be forwarded to the Sponsor.

8 Adverse Event Reporting

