7.4 Visit Schedule and Procedures

7.4.1 Visit 0: Baseline /Screening Visit

Procedures to be Performed

The following evaluations will be performed to assess eligibility according to the Inclusion and Exclusion Criteria at the baseline visit only:

1. The patient is expected to attend the baseline visit not wearing their habitual contact lens products.
 2. The subject will be required to read and sign an Informed Consent Form prior to enrolment. When the subject has signed the consent form, the subject will be considered to be enrolled on to the study.
 3. Participant demographics (age, sex, medications, allergies) will be recorded.
 4. Habitual lens wearing time (average, maximum, average comfortable) will be recorded.
 5. [REDACTED]
 6. Auto Refraction/Auto Keratometry: steepest and flattest K readings (mm).
 7. Pupil Sizes in High and Low Illumination will be measured using the Neuroptics pupilometer while looking in the distance.
 8. Sphero-cylindrical refraction will be conducted
 9. Visual Acuity will be assessed with be assessed with Sphero-cylindrical refraction (D)
 - a. Distance visual acuity
 - i. High Illumination High Contrast (OU)
 - ii. High Illumination Low Contrast (OD, OS, OU)
 - iii. Low Illumination High Contrast (OD, OS, OU)
 - b. Near visual acuity
 - i. High Illumination High Contrast (OU)
 - ii. Low Illumination High Contrast (OU)
- High Illumination: Overhead lights on, Ideal: 60cd/m², Range: 120-200cd/m²
- Low Illumination: Overhead lights off, Ideal: Ideal: 3cd/m², Range: 1-5cd/m²
10. Slit lamp biomicroscopy will be assessed according to the guidelines set out in the CVI Grading scales.

11. The investigator will confirm that the patient meets the criteria set out in the inclusion criteria.

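### The same-day rule for Visits 0 and 1 waives the only visible per-eye, high-illumination, high-contrast spectacle acuity reading taken before lens wear

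*Combined protocol and SAP*

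**What the plan says.** Section 7.4.2 (Visit 1) opens with the rule "Dispensing visit may occur on same day as Visit 0. In which case, steps 1,2 &3 are redundant". Step 1 is "Entrance distance HHHC VA (OD, OS) with best spherocylindrical correction". Step 2 is slit lamp biomicroscopy and step 3 is confirmation of eligibility.

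Section 7.4.1 (Visit 0), step 9, measures acuity with the sphero-cylindrical refraction. Its three distance lines are "High Illumination High Contrast (OU", "High Illumination Low Contrast (OD, OS, OU" and "Low Illumination High Contrast (OD, OS, OU" (closing brackets not shown). The first is binocular only; the other two are per eye and binocular. Step 10 reads "Slit lamp biomicroscopy will be assessed according to the guidelines set out in the CVI Grading scales" and step 11 reads "The investigator will confirm that the patient meets the criteria set out in the inclusion criteria".

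Section 7.4.4 (Visit 3), step 10, takes exit HHHC distance acuity in logMAR, through the baseline refraction, for the right eye, the left eye and both together.

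Section 8.1 defines adverse event codes 02 and 16 by a loss of at least 2 lines of best spectacle-corrected acuity, permanent for code 02 and lasting at least 2 weeks for code 16. Section 8.2 asks for a separate form for each eye when both are involved.

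**The concern.** A step is redundant only if its information already exists. That is true of steps 2 and 3. It is not true of step 1, because no visible Visit 0 step takes this acuity in each eye separately. If the rule is followed as written, a same-day subject starts lens wear without the per-eye entrance reading that the per-eye exit reading would be compared with.

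What is at stake is the per-eye acuity safety record. A loss can be confined to one eye, and a binocular reading is a poor reference for it because the better eye can mask the change. A pre-wear reading cannot be recovered after wear has begun. The link to codes 02 and 16 is inferred: the documents do not say which reading is the reference for lines lost.

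**Working it through.** The plan gives no figure to reproduce, so the check compares the visit schedules.

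**1. Are the waived steps duplicated at Visit 0?**

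- Step 2, slit lamp: yes, Visit 0 step 10. Step 2.a and the footnote to Table 2 give the same waiver.
- Step 3, eligibility: yes, Visit 0 step 11.
- Step 1, HHHC acuity, right and left eye, spectacle correction: no. Visit 0 step 9.a.i is binocular only.

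So 2 of the 3 waived steps are duplicated and 1 is not. OU at step 9.a.i cannot easily mean each eye in turn, because the next two lines of the same list write OD, OS, OU.

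**2. Which exit readings have a like-for-like pre-wear value?** HHHC is not spelled out in the visible text; it is read here as high illumination, high contrast. Visible distance readings in that condition, with spectacle correction:

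| | Right eye | Left eye | Both eyes |
|---|---|---|---|
| Before wear, same-day path | 0 | 0 | 1 (Visit 0) |
| Before wear, separate-day path | 1 (Visit 1 step 1) | 1 (Visit 1 step 1) | 1 (Visit 0) |
| Exit, all subjects | 1 | 1 | 1 |

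Matched exit readings: same-day 1 of 3 (0 of 2 per eye); separate-day 3 of 3.

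**3. Does a later visit fill the gap?** Distance listings of this condition before exit step 10 on the same-day path:

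- Visit 0: step 9.a.i (1)
- Visit 1: steps 7 and 11 (2)
- Visit 2: steps 5, 6, 14 and 18 (4)
- Visit 3: steps 5 and 6 (2)

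1 + 2 + 4 + 2 = 9, all marked OU. Step 6 at Visits 2 and 3, for example, is "Monocular over-refraction and High Illumination High Contrast logMAR VA @ 4m (OU) will be performed and recorded". Eight of the nine are with study lenses. Visits 2 and 3 carry a general note that ocular measurements are made on each eye, but any reading it adds would be with study lenses and after wear had begun.

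**4. How many eyes?** Eyes without the reading = 2 × 50 completers × same-day share. The share is not stated. Assumed 0%, 50%, 100%: 0, 50, 100 eyes.

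**5. How far does the eligibility criterion help?** Section 7.2 requires 20/25 or better in each eye with habitual correction, or 20/20 best corrected. Assume 0.1 logMAR per line, and acuity through the baseline refraction no worse than with habitual correction.

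- 20/25 = log10(25/20) = 0.097, about 0.1. An exit reading of 0.1 + 0.2 = 0.3 or worse (20/40 = 0.301) is then a loss of at least 2 lines whatever the start.
- If the best plausible start is S, an exit reading better than S + 0.2 is certainly not such a loss.
- Exit readings from S + 0.2 to just under 0.3 stay unsettled.

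| Assumed best start S (logMAR) | Unsettled, 20/25 route | Width | Width, 20/20 route (upper limit 0.2) |
|---|---|---|---|
| 0.0 | 0.2 to <0.3 | 0.1 | 0 |
| -0.1 | 0.1 to <0.3 | 0.2 | 0.1 |
| -0.2 | 0.0 to <0.3 | 0.3 | 0.2 |

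The criterion catches large losses but not a 2-line fall from a better-than-threshold start.

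**The case against.** The strongest reply is that step 9.a.i is simply an incomplete eye list. Calling step 1 redundant presupposes that the data exist; eligibility is set per eye, so some per-eye acuity must be seen at Visit 0; and Table 2 places spectacle-corrected logMAR acuity there. That is plausible. But no visible step records the per-eye value, and the binocular-only marking recurs at every study-lens listing of the condition. If it is a slip, the text still has to be corrected, because sites follow the list as printed.

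Second, the adverse event consequence is limited. Each lens period is 3 days plus up to 2, so exit falls at most about 2 × 5 = 10 days after Visit 1. The exit reading alone cannot show a permanent loss or one lasting 2 weeks; both need follow-up, which section 8.2 requires until resolution. For a temporary loss, the recovered acuity gives a retrospective reference. This stands, and leaves code 02 as the main exposure.

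Third, each eye's start is partly bracketed. Steps 9.a.ii and 9.a.iii give four per-eye pre-wear readings, which bound the worst start if lower contrast or light does not improve acuity. The binocular reading bounds the best start if an eye is rarely better alone than with its fellow. This also stands and would narrow the unsettled ranges for individual subjects. None of these readings is taken in the exit condition for one eye, so they do not replace the missing value.

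Fourth, HHHC is undefined and Visit 0 step 5 is redacted. Step 5 comes before the refraction at step 8, so it is unlikely to be acuity through that refraction, but this cannot be confirmed. The finding is limited to visible text.

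**Conclusion.** The concern holds and is minor. On the visible text, the same-day rule drops one step that Visit 0 does not duplicate, and both per-eye exit readings lose their like-for-like pre-wear value. Separate-day subjects and the binocular exit reading are unaffected.

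The number of eyes is 0 to 100 among about 50 completers, depending entirely on the unstated same-day share. It counts missing readings, not misclassified events; the number of eyes with a true 2-line loss cannot be estimated from the documents. The conclusion rests on reading HHHC as high illumination, high contrast, and on the redacted step not supplying the reading. No stated hypothesis or analysis is affected: the slit-lamp comparison and the comparison of acuity between lenses do not use this value.

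**What to change.** Reconcile sections 7.4.1, 7.4.2 and 7.4.4 by one of two changes:

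- list right eye, left eye and both eyes at Visit 0 step 9.a.i; or
- limit the same-day waiver in section 7.4.2 to steps 2 and 3, so that step 1 is always done.

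Then check Table 2 against the choice: its spectacle-acuity row is blank (a dash) at Visit 1 although step 1 is scheduled there on the separate-day path.

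The cost is a one-line text change and two extra chart readings per same-day subject, with a measurement already in the protocol and at a visit already under way (assumed 1 to 2 minutes). The change has to be in place before subjects are dispensed lenses, because the reading cannot be taken afterwards.

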8.1 Adverse Event Definitions

An 'adverse event' refers to any undesirable clinical occurrence in a participant, whether it is considered to be device-related or not. Adverse events (AE) may be classified as 'unanticipated adverse device effects,' 'serious adverse events,' 'significant adverse events,' or 'non-significant adverse events,' as defined below.

| Classification | Definition |
|-------------------------------------|---|
| Serious Adverse Event | Those events that are life-threatening, or result in permanent impairment of a body function, or permanent damage to a body structure or necessitate medical (therapeutic) or surgical intervention to preclude permanent impairment of a body function or permanent damage to a body structure. |
| Significant Adverse Event | Those non-serious adverse events that occur with contact lens usage that are not sight-threatening but are usually symptomatic and may warrant therapeutic management and /or temporary or permanent discontinuation of contact lens wear. |
| Non-Significant Adverse Events | Those less severe non-serious adverse events that occur with contact lens usage that are not sight-threatening, may or may not be symptomatic and may warrant palliative management, such as ocular lubricants or temporary interruption of contact lens wear. |
| Unanticipated Adverse Device Effect | Adverse events in a clinical trial that were not previously identified in the protocol in terms of nature, severity, or degree of incidence. An Unanticipated Serious Adverse Device Effect is an unanticipated adverse event that is serious in nature and caused by or associated with the device and is considered reportable. |

AE classification, coding (for reporting to the sponsor) and examples are provided in the following table of Contact Lens Adverse Event Classification and Reporting table:

| Code | Condition | Reporting |
|---------------------------------------|---|--|
| Serious Adverse Events | | |
| 01 | Presumed infectious keratitis or infectious corneal ulcer | Notify sponsor as soon as possible, within 24 hours ; IRB reporting as per requirements |
| 02 | Permanent loss of ≥ 2 lines of best spectacle corrected visual acuity (BSCVA) | |
| 03 | Corneal injury that results in permanent opacification within central cornea (6mm) | |
| 04 | Uveitis or Iritis (e.g. presence of anterior segment inflammation as described in ISO 11980, Annex B) | |
| 05 | Endophthalmitis | |
| 06 | Hyphema | |
| 07 | Hypopyon | |
| 08 | Neovascularization within the central 6mm of cornea | |
| 00 | Other serious event | |
| Significant Adverse Events | | |
| 11 | Peripheral (outside central 6mm), non-progressive, non-infectious ulcer | Notify sponsor as soon as possible, within 5 working days ; IRB reporting as per requirements |
| 12 | Symptomatic corneal infiltrative event | |
| 13 | Superior epithelial arcuate lesions (SEALs) involving epithelial split | |
| 14 | Corneal staining \geq dense coalescent staining up to 2mm in diameter (e.g. moderate, ISO 11980 grade 3) | |
| 15 | Corneal neovascularization ≥ 1.0 mm vessel penetration (e.g. \geq ISO 111980 Grade 2), if 2 grade change from baseline | |
| 16 | Any temporary loss of ≥ 2 lines BSCVA for ≥ 2 wks | |
| 17 | Any sign and/or symptom for which subject is administered therapeutic treatment or which necessitates discontinuation of lens wear for ≥ 2 weeks | |
| 10 | Other significant event | |
| Non-significant Adverse Events | | |
| 21 | Conjunctivitis (bacterial, viral or allergic) | |

| | | |
|----|--|--|
| 22 | Papillary conjunctivitis if \geq mild scattered papillae/follicles approximately 1mm in diameter (e.g. ISO 11890 Grade 2), if 2 grade change from baseline | Notify sponsor as soon as possible, within 5 working days ; IRB reporting as per requirements |
| 23 | Asymptomatic corneal infiltrative events | |
| 24 | Any sign and/or symptom for which temporary lens discontinuation for > 1 day is recommended (if not already classified) | |
| 20 | Other sign and/or symptom warranting classification as a non-significant adverse event | |

Normal or adaptive symptoms

Transient symptoms such as end-of-day dryness, lens awareness, itching or burning or other discomfort may occur with contact lens wear and may occasionally reduce wearing time. **These are not reported as adverse events unless in the investigator’s opinion they are unexpected in nature, severe or have a high rate of occurrence.**

